Baseline Comparability, Reach, and Representativeness. We will examine baseline differences across groups in measures of study endpoints as well as other potential prognostic indicators, such as patients' age, comorbid diagnoses, and history of pain treatment. Any differences across groups in baseline characteristics will be controlled statistically in analyses comparing outcomes. The RE-AIM framework is a methodology for systematically considering all strengths and weaknesses of an intervention in order to better guide program planning.⁸³ To evaluate reach, we will ask patients who decline study participation whether they would be willing to provide informed consent to participate in a brief survey that identifies their reasons for declining participation and the characteristics that differentiate them from enrollees.

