Intensity of Service Use (Specific Aim 2). We will compare service utilization by category (e.g., CBT therapist time, PCP visits, and pharmacy use) between groups. We will conduct a budget impact analysis⁸⁴ and will include the cost of the intervention (personnel, supplies, CBT therapist training, and IVR fixed/variable costs) as well as costs for specific medical care services likely to be affected. Data from CBT therapists time records will be combined with wage data from the VA Financial Management System to produce estimates of intervention-specific personnel costs. Costs associated with the use of specific medical care services, such as medications, will be obtained from the Decision Support System (DSS) files. Cost analysis will be conducted in accordance with the guidance provided by Mauskopf et al.⁸⁴ including the use of sensitivity analysis and scenarios that allow for varying assumptions about intervention uptake, compliance or component costs. All resource use and cost comparisons will be adjusted for any

observed differences in baseline characteristics. Because costs of resource utilization are usually skewed, alternative modeling techniques (e.g., log-transformed costs, negative binomial regression) will be used.

Intervention Engagement and Satisfaction with Care (Specific Aim 3). As in our prior research,⁴⁹ we will conduct extensive analyses of the process of intervention delivery in both arms. We will monitor the proportion of telephone CBT sessions that are completed, and we will determine the patient and session characteristics associated with patients' reports of skill practice. Patients in the AI-CBT group will report their satisfaction with aspects of the intervention (e.g., whether it provided information useful for achieving behavioral targets), and we will assess the correlation between satisfaction ratings and measures of: intervention engagement, patients' baseline characteristics, and changes in pain-related functioning. Differential dropout across groups will be examined using Kaplan-Meier curves and survival models.

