Resource Use (Aim 2). Intervention Costs. Therapists will use a log to record time spent in intervention-related activities for a random 20% of all treatment days. Time records will be combined with wage data from the VA Financial Management System to estimate intervention-specific personnel costs. Technology costs of the AI-CBT program include fixed costs (e.g., software development and computer maintenance) plus variable costs (e.g., minute costs for IVR calls). One-time fixed start-up costs will be reported separately. VA Inpatient and Outpatient Service Use data will be obtained from the Musculoskeletal Diagnoses Cohort (MSD), a project currently underway as part of the VA Connecticut Healthcare System's CREATE. The MSD is developing validated algorithms for using VA electronic health record data to identify utilization events, comorbid conditions, receipt of opioid medications, and pain screening results, for patients with pain-related diagnoses. Information on non-VA admissions will be collected by the patient survey. To mitigate recall bias, we will use a two-time frame method that asks about utilization over the past 6 months and over the past 2 months with more weight given to the shorter timeframe.⁷⁶

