Demographics and Other Covariates Measured at Baseline. We will measure patients' baseline Sociodemographic and Pain Characteristics that have been shown to be associated with treatment outcomes, e.g., age, gender, education level, racial/ethnic background, marital status, occupational status, pain duration, and number and location of pain sites. We also will gather data on participants' level of health literacy.⁷⁹ Pain Classification will be derived through a systematic evaluation of each enrolled participant's EMR using an assessment tool based on clinical guidelines for diagnosing and treating low back pain.¹ Pain classes will include non-specific low back pain, low back pain with a radicular component, or low back pain associated with other specific spinal causes. A nurse practitioner, who is supported by the West Haven COIN and who has been trained to use this tool and is using it in our trial IIR 09-058, will conduct the assessment. She will be supervised by a pain medicine physician ([name]) who will review ten percent of the classification ratings for accuracy and provide corrective feedback if necessary. Psychiatric and Substance Abuse Comorbidities will be measured using medical record diagnoses and mental health encounters. Additional self-report information will be collected using subscales of the Mini International Neuropsychiatric Interview (MINI)⁶¹ related to mood and substance abuse disorders. Pain Medication Use will be assessed through patient survey and a review of computerized pharmacy records. Pain medication will be coded as non-steroidal anti-inflammatory, non-narcotic analgesics, narcotic analgesics, and benzodiazepines and other sedative/hypnotics. For each category, we will document post-treatment whether patients have experienced an increase, no change, or decrease in their medication use. Distance from VA will be calculated and used as a measure of geographic access. The Pain Catastrophizing Scale is a 13-item self-report scale that examines thoughts and feelings people may experience when they are in pain including rumination, magnification, and helplessness.⁸⁰ Finally, Pain-related Fear will be measured using the Tampa Scale of Kinesiophobia-revised (TSK-R), which has two subscales (Fear of Harm/Activity Avoidance and Pathophysiological Beliefs) and has been shown to be sensitive to treatment-related change.

Methods for Dealing with Data Transformations

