We will examine the distribution of all study variables to assess extreme values, missing data, variances, skewness, and type of distribution. Preliminary analyses will examine the distributions of variables to assess deviations from normality and other deviations from assumptions of the planned statistical analyses. Outliers will be corrected. Transformations of the data will be conducted if appropriate to obtain normality of residuals.

Definitions of the Analytical Sets

Baseline Comparability, Reach, and Representativeness. We will examine baseline differences across

groups in measures of study endpoints as well as other potential prognostic indicators, such as patients' age, comorbid diagnoses, and history of pain treatment. Any differences across groups in baseline characteristics will be controlled statistically in analyses comparing outcomes. The RE-AIM framework is a methodology for systematically considering all strengths and weaknesses of an intervention in order to better guide program planning.⁸³ To evaluate reach, we will ask patients who decline study participation whether they would be willing to provide informed consent to participate in a brief survey that identifies their reasons for declining participation and the characteristics that differentiate them from enrollees.

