Analysis of Endpoints (addressing Specific Aim 1). We will test for non-inferiority of AI-CBT compared to standard telephone CBT at 12 weeks by comparing the upper limit of the two-sided 95% confidence interval for the difference in the mean RMDQ scores, calculated as AI-CBT minus standard CBT, to the pre-set non-inferiority margin of 2 points in RMDQ and will conclude that AI-CBT is non-inferior if the upper limit is less than 2. Because intent-to-treat analysis can raise the risk of type I error in a non-inferiority trial,⁸¹ we will conduct both a per protocol and intent-to-treat analysis. The "per protocol" group assignment will be defined as completing four or more CBT sessions (either IVR or "live" sessions); however, we will revisit this definition with the Expert Panel prior to the start of the trial. We will declare AI-CBT non-inferior to standard CBT only if AI-CBT is shown to be non-inferior using both the intention-to-treat and per-protocol analysis sets. We expect that RMDQ scores will be normally distributed. If not, we will use transformations to achieve normality. We also will develop a two-level linear mixed-effects model that uses RMDQ follow-up scores at both assessment times (three and six months) as the dependent variables; treatment group, time and the treatment by time interaction as categorical explanatory variables; and baseline RMDQ score as a continuous covariate. If this model shows no significant time by group effect, we can drop the interaction term and test for the time-averaged non-inferiority of AI-CBT compared to standard CBT between 3 and 6 months. This model will also allow for adjustment for design-related factors (e.g., site and age). An unstructured variance-covariance matrix will be used to model the error variance. Secondary outcomes including pain intensity, emotional functioning, global perception of change, and quality of life will be analyzed in a manner similar to that used for the primary outcome. Analyses of all other outcomes will be conducted on an intent-to-treat basis.

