Intensity of Service Use (Specific Aim 2). We will compare service utilization by category (e.g., CBT therapist time, PCP visits, and pharmacy use) between groups. We will conduct a budget impact analysis⁸⁴ and will include the cost of the intervention (personnel, supplies, CBT therapist training, and IVR fixed/variable costs) as well as costs for specific medical care services likely to be affected. Data from CBT therapists time records will be combined with wage data from the VA Financial Management System to produce estimates of intervention-specific personnel costs. Costs associated with the use of specific medical care services, such as medications, will be obtained from the Decision Support System (DSS) files. Cost analysis will be conducted in accordance with the guidance provided by Mauskopf et al.⁸⁴ including the use of sensitivity analysis and scenarios that allow for varying assumptions about intervention uptake, compliance or component costs. All resource use and cost comparisons will be adjusted for any observed differences in baseline characteristics. Because costs of resource utilization are usually skewed, alternative modeling techniques (e.g., log-transformed costs, negative binomial regression) will be used.

Intervention Engagement and Satisfaction with Care (Specific Aim 3). As in our prior research,⁴⁹ we will conduct extensive analyses of the process of intervention delivery in both arms. We will monitor the proportion of telephone CBT sessions that are completed, and we will determine the patient and session characteristics associated with patients' reports of skill practice. Patients in the AI-CBT group will report their satisfaction with aspects of the intervention (e.g., whether it provided information useful for achieving behavioral targets), and we will assess the correlation between satisfaction ratings and measures of: intervention engagement, patients' baseline characteristics, and changes in pain-related functioning. Differential dropout across groups will be examined using Kaplan-Meier curves and survival models.

Preplanned Subgroup Analysis. Because AI-CBT will continue to learn patterns in patients' experience throughout the intervention period, we hypothesize that the second 50% of patients randomized will show

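### Aim 2 service-use and cost models choose covariates by observed baseline imbalance, with no threshold and no fixed set, so precision that prior use could supply may be lost

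*Combined protocol and SAP*

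**What the plan says.** Protocol section D.9 and the SAP carry the same paragraph on Intensity of Service Use (Specific Aim 2). The outcomes are set out as: "We will compare service utilization by category (e.g., CBT therapist time, PCP visits, and pharmacy use) between groups". VA care costs are added for the budget impact analysis. The only statement on covariates is "All resource use and cost comparisons will be adjusted for any observed differences in baseline characteristics".

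The paragraph on Baseline Comparability, in D.9 and in the SAP, applies the same approach to every outcome: "Any differences across groups in baseline characteristics will be controlled statistically in analyses comparing outcomes". The characteristics to be examined are endpoint measures and other prognostic indicators, "such as patients' age, comorbid diagnoses, and history of pain treatment". Neither place says how large a difference must be, or how it is judged.

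The Aim 1 mixed model is handled differently. It has treatment, time and their interaction, "and baseline RMDQ score as a continuous covariate", whatever the baseline balance, and it allows for site and age.

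On data sources, the SAP section Resource Use (Aim 2) takes VA service use from the Musculoskeletal Diagnoses Cohort: "The MSD is developing validated algorithms for using VA electronic health record data to identify utilization events, comorbid conditions, receipt of opioid medications". Costs come from the Decision Support System (DSS) files. Among the baseline covariates, the SAP says: "Pain Medication Use will be assessed through patient survey and a review of computerized pharmacy records".

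**The concern.** Under randomisation, a covariate improves precision because it predicts the outcome. Whether the arms happen to differ on it in one trial is a separate matter. A rule keyed to imbalance therefore selects on the wrong property, and a strong predictor that is well balanced can be dropped. Site and age group illustrate this: randomisation is blocked on both, so they are balanced by design and would seldom qualify.

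For visits, prescriptions and VA costs, the natural predictor is the same patient's use in the same category before randomisation. No Aim 2 model names it.

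At stake is the width of the intervals for overall ambulatory, inpatient and pharmacy use, which Aim 2 sets out to compare and which feed the budget impact analysis. The plan also leaves open which covariates the reported estimate will carry.

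**Working it through.** **1. The plan's own figure.** Aim 2 has no stated power or precision. The only sample-size calculation is for the RMDQ: margin 2, SD 4.5, true difference 0, one-sided 0.025, power 90%, ratio 1.37:1.

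n(control) = (1 + 1/1.37) × 4.5² × (1.960 + 1.282)² / 2² ≈ 92.0, taken up to 93. n(AI-CBT) = 1.37 × 93 = 127.4, taken up to 128. The total of 221 agrees with the plan, and noncentral-t power at 128:93 is 90.1%. For 20% dropout, 128/0.8 = 160 and 93/0.8 = 116.25, taken up to 117, which gives the SAP's 277. The protocol has 278 (160:118), which makes no practical difference here.

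**2. Unadjusted precision for an Aim 2 mean.** SE = SD × √(1/160 + 1/118) = 0.121 SD. The difference detectable with 80% power at two-sided 5% is (1.960 + 0.842) × 0.121 = 0.34 SD.

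**3. Gain from always adjusting.** Let ρ be the correlation between prior and follow-up use. The documents do not give it, so 0.3 to 0.7 is an assumption. Residual variance is multiplied by 1 − ρ² and the interval width by √(1 − ρ²). Adjusted power = Φ[(z + 1.96)/√(1 − ρ²) − 1.96], where z is the normal quantile of the unadjusted power.

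| ρ (assumed) | 1 − ρ² | Interval narrower by | 278/(1 − ρ²) | Power, from 60% | Power, from 80% |
|---|---|---|---|---|---|
| 0.3 | 0.91 | 4.6% | 305 | 64% | 83.6% |
| 0.5 | 0.75 | 13.4% | 371 | 72% | 89.9% |
| 0.7 | 0.51 | 28.6% | 545 | 87% | 97.5% |

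The fourth column is the number of unadjusted patients giving the same precision. The 60% and 80% starting points are illustrations, since the plan has no Aim 2 effect size.

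**4. What a significance trigger would do.** With random allocation, a baseline test falls below its threshold by chance in that share of trials. One given covariate therefore enters in about 5%, 10% or 20% of trials at p<0.05, p<0.10 or p<0.20, and is left out in the other 95%, 90% or 80%. A simulation (8,000 trials per setting, 160:118, normal outcome, true difference 0.34 SD) gave this power:

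| ρ | Adjust if p<0.05 | Adjust if p<0.20 | Always adjust |
|---|---|---|---|
| 0.3 | 79% | 81% | 82–84% |
| 0.5 | 80% | 83% | 90% |
| 0.7 | 81% | 86% | 97% |

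With no true difference, two-sided type I error at ρ = 0.3, 0.5 and 0.7 was 4.9%, 4.3% and 3.6% for the p<0.05 trigger, and 4.2%, 3.5% and 2.5% for p<0.20. The triggered rule is conservative.

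**5. Skewed costs.** With lognormal costs (log SD 1), ρ = 0.5 on the log scale and 160:117 patients, power was 64% unadjusted, 65% with the p<0.05 trigger and 72% always adjusted. That model has no zero costs.

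**6. Rare events.** Assume 0.1 admissions per patient over 6 months of follow-up, 0.2 over a 12-month look-back, and a stable patient-level rate with gamma variance v. Then ρ = 0.1 × 0.2 × v / √[(0.1 + 0.01v)(0.2 + 0.04v)].

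- v = 1: 0.02/√(0.11 × 0.24) = 0.12, interval about 1% narrower.
- v = 2: 0.04/√(0.12 × 0.28) = 0.22, about 2% narrower.
- v = 4: 0.08/√(0.14 × 0.36) = 0.36, about 7% narrower.

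**The case against.** **The trigger is not in the plan.** A reader might infer that prior use will usually be dropped. The documents do not support that as a fact, because no p-value or other threshold appears. Read literally, nearly every numerical difference would qualify and nearly every examined characteristic would enter. History of pain treatment is on that list, so something close to prior use might be among them. This objection stands, and the 95% and 80% figures hold only if a significance-type trigger is used. The literal reading does not repair the plan, however: prior use or cost in the same category is still not named, the list of characteristics is open-ended, and the set is fixed only after baseline data are seen.

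**The data may not be in hand.** A reader might also infer that the trial already holds prior use. Identification of patients reads pain scores at outpatient encounters in the past year, but does not tabulate visits or cost. Medication use is coded by drug category and direction of change, which gives neither volume nor cost. The utilisation algorithms are described as still in development. A pre-enrolment extract is plausible from these sources, but it is not stated.

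**The size is assumed.** No ρ, Aim 2 effect or Aim 2 power is given. At ρ = 0.3 the gain is small, and for admissions it may be negligible. This stands.

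**The lead quantity is untouched.** Aim 2 puts therapist time first, and it has no pre-enrolment counterpart. The budget impact analysis also varies uptake, compliance and component costs in scenarios. This limits the importance of the point, though Aim 2 also names overall ambulatory and inpatient use.

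**Conclusion.** The concern holds as a matter of precision and pre-specification in secondary comparisons that have no stated power. Aim 2 selects covariates by observed imbalance, with no threshold and no fixed set, although the Aim 1 mixed model in the same plan always carries the baseline value of its outcome.

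The loss is conditional on two assumptions: that a significance-type trigger is used, and that prior and follow-up use are correlated at about 0.3 to 0.7. It is minor at the low end and material from about 0.5, for categories used often enough to support such a correlation.

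The documents do not support reading this as bias, as inflated type I error, as a flaw in the therapist-time comparison, or as a criticism of the 12-week RMDQ test. It is a cheap improvement and does not threaten the trial's conclusions.

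**What to change.** In D.9 and in the SAP, under Intensity of Service Use (Specific Aim 2), replace the adjustment sentence for VA outpatient, pharmacy and inpatient use and cost with a fixed covariate set entered in every model regardless of balance:

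- the randomisation strata: site, and age <65 versus ≥65;
- use or cost in the same category before randomisation, over one pre-specified look-back (for example 12 months), from the same VA record, pharmacy and DSS sources as the follow-up data.

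Report the unadjusted comparison as a sensitivity analysis. State that this set takes precedence over the general rule under Baseline Comparability for these outcomes.

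The cost is a change of SAP wording, one further data pull that is not yet planned, and a little data management. No extra patients, visits or staff are needed. If the extract proves unavailable for a category, the strata can still be fixed in advance.
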